5.4. Discharge / transfer to another hospital prior to written consent

It is expected that consent will be sought for all participants prior to discharge/transfer to another hospital.

In the rare instances where consent is not sought prior to discharge/transfer, the following should occur:

The Research Midwife (RM), or other designated member of the research team at site, will call the participants within 5 working days of randomisation to inform them and/or their family of the participant's involvement in the trial and provide details of the trial.

Once the telephone call has been completed, the RM, or other designated member of the research team at site, will post/email within 5 working days as applicable:

- Participant covering letter to home/email address
- Participant information sheet and consent form to home/email address

The covering letter will confirm that the participant has 4 weeks from the date of the letter to return the consent form confirming whether they would like to continue participation in in the trial.

If no response is received within 2 weeks (14 days), the RM, or other designated member of the research team at site will make a follow up call to the participant to check that they have received the information and request that the consent form be returned within 5 working days if they would like to continue participation in the trial. Written information and a consent form will be re-sent if the site team member is unable to contact the participant, or information has not been received.

If no response is received within 4 weeks (28 days), the participant's data will not be included within the trial as confirmed in the telephone conversation/covering letter. Consent is being sought in this scenario for the disclosure of confidential information in order to avoid a breach of the common law duty of confidentiality. If we find that consent in this scenario is not practicable and results in informative missing data (e.g. linked to severity of condition or duration of hospital stay) a future Section 251 application may be made for future participants.

5.5. Maternal death prior to written consent

This is likely to be a very rare occurrence.

All deaths, for women who have verbally consented should be reported on a Serious Adverse Event CRF and faxed to the Clinical Trials Office within 24 hours of the research team becoming aware.

5.6. Neonatal death prior to written consent

This is likely to be a rare occurrence.

Consent will be sought if considered appropriate; however, it is at the discretion of the site staff to determine if this is appropriate for each individual participant. In this situation, the usual information sheet and consent form would be used.

6. IDENTIFICATION, SCREENING, ENROLMENT AND RANDOMISATION

6.1. Identification

Identification of participants will be by the clinician performing the rotational birth, as described in the Consent section (section 5) of this protocol. The clinician will also confirm eligibility.

Following automated randomisation, the local PI, Research Midwife, or delegated members of the local team, will obtain postnatal written consent prior to discharge, normally within 24-48 hours.

6.2. Enrolment

Enrolment will take place upon confirmation of eligibility and verbal consent of the woman taken by the clinician performing the rotational birth.

Details of all patients approached about the trial for verbal consent will be recorded on the ROTATE **Participant Eligibility Log** which will be kept in the ISF, and should be available to be sent to the Trials Office upon request.

If a woman with a relative contraindication (section 7.2) is considered ineligible by the clinician assessing eligibility, this decision and reason will be recorded in this Participant Eligibility Log and the case report form (CRF) will capture the reason.

If women with these conditions (suspected fetal bleeding disorder / suspected fetal predisposition to fracture / blood borne viral infection) are excluded this will be recorded in the Participant Eligibility Log.

6.3. Randomisation

Randomisation must be able to take place at any time of day, therefore a 24-hour telephone and online randomisation service is provided by the Health Services Research Unit at the University of Aberdeen available at https://w3.abdn.ac.uk/hsru/ROTATE. Unique log-in usernames and passwords will be provided to those who wish to use the online randomisation system and who have been delegated the role of randomising participants into the trial as detailed on the ROTATE Site Signature and Delegation Log. The randomisation system is available 24 hours a day, 7 days a week, apart from short periods of scheduled maintenance. A telephone toll-free randomisation service [name] is available 24-hours, seven-days a week.

6.3.1. Randomisation Process

After participant eligibility for randomisation has been confirmed and informed verbal consent has been given, the participant can be randomised into the trial. Randomisation Forms will be provided to investigators and may be used to collate the necessary information prior to randomisation. All questions and data items on the Randomisation Form must be answered prior to a potential participant being randomised into the trial and a Trial Number being issued.

Following randomisation, a confirmatory e-mail will be sent to the nominated email address(s). This can be, but not exclusive to, the local PI, research midwife, or research mailbox.

The local research team should add the participant to the **Participant Recruitment and Identification Log**, which links participants with their allocated trial number. PIs (or their delegates) must maintain this document securely, and which is **not** for submission to the Trials Office. The **ROTATE Participant Recruitment and Identification Log** should be held in strict confidence.

6.3.2. Randomisation Method

Participants will be randomised by telephone and online at the level of the individual in a 1:1 ratio to either manual or instrumental rotation.

A minimisation algorithm will be used within the randomisation system to ensure balance in the treatment allocations over the following variables:

- Centre
- Position
 - Occipito-Transverse: occiput between 8 to 10 o'clock or 2 to 4 o'clock
 - Occipito-Posterior: occiput between 4 and 8 o'clock (diagrams will be provided to standardise the classification)

6.4. Blinding

This is not a blinded trial because it is not pragmatic to blind the rotational methods; therefore there will be no procedures for unblinding.

6.5. Informing the Participant's GP and Other Parties

No other parties outside of the trial team will be informed of the participant's entry into the study. Participants can inform their GP if they wish.

7. TRIAL INTERVENTION

7.1. Trial Intervention(s)

INTERVENTION – MANUAL ROTATION

Rotation of the fetal head by manual rotation - followed by direct forceps or direct ventouse or maternal effort. The instrument to be used for direct traction after the rotation is at the choice of the obstetrician and will be recorded for further analysis on the Day 0 CRF.

COMPARATOR – INSTRUMENTAL ROTATION

Rotation of the fetal head by rotational instrument (rotational forceps or rotational ventouse) at the choice of the obstetrician.

Instrument to be used for direct traction after the rotation at the choice of the obstetrician – usually the same type of instrument (forceps or ventouse), but use of maternal effort after rotation by instrument is also possible.

STANDARDISATION OF INTERVENTIONS

Obstetricians taking part in the study and performing the rotational births will be Good Clinical Practice (GCP) trained and competent (trainees signed-off as competent on the national RCOG trainees' logbook; and consultants agreed as competent by PI in each site at the site initiation training) in both manual rotation and at least one rotational instrument; or they will be supervised directly by someone competent and GCP trained.

Rotation from occipito-transverse or left occipito-posterior /right occipito-posterior to a direct occipito-posterior position prior to operative delivery will be discouraged in the site-specific visits/ site initiation training. We will collect relevant data in the Day 0 CRF for analysis as needed, including if such rotation was accidental or performed on purpose.

The site initiation training will include a standardisation educational session for manual rotation and diagnosis of anal sphincter injury.

7.2. Contraindications

Women with contraindications for operative birth with either ventouse or forceps as per national RCOG guidance (21) will not be eligible:

Contraindications to either ventouse/vacuum or forceps

• Forceps and vacuum extraction are contraindicated before full dilatation of the cervix.

Contraindications to ventouse/vacuum alone

• The vacuum extractor is contraindicated with a face presentation.

Note: Women with pregnancies under 36 weeks' gestation are excluded from the trial – see Section 4: Eligibility.

The following are not absolute contraindications:

- Suspected fetal bleeding disorders or a predisposition to fracture are relative contraindications to assisted vaginal birth with either ventouse or forceps. However, there may be considerable risks if the fetal head has to be delivered abdominally from deep in the pelvis. Experienced obstetricians should be involved in the decision-making for exceptional indication. Low forceps may be acceptable for assisted vaginal birth with suspected fetal bleeding disorders, but vacuum extraction should be avoided.
- Blood borne viral infections in the woman are not an absolute contraindication to assisted vaginal birth. However, it is sensible to avoid difficult assisted vaginal birth where there is an increased chance of fetal abrasion or scalp trauma.

Note: The use of a vacuum is not contraindicated following a fetal blood sampling procedure or application of a fetal scalp electrode as per national guidance (RCOG).

7.3. Intervention Modification

Changes from the allocated intervention will be documented, alongside possible reasons:

Participant refusal to allow the randomised intervention – with reasons and detail of the discussion with the accoucheur/midwife.

7.4. Accountability

We will capture data with a dedicated **ROTATE Manual Rotation Checklist** on the conduct of steps essential to the manual rotation technique.

7.5. Adherence & Cross-over

Adherence to the intervention, modifications, and their reasons, will be recorded on a dedicated **Adherence Checklist on the CRF**:

- I) Randomised Technique
- II) Rotational Technique used first reasons why/if different from I
- III) Rotational Technique used second if the first failed
- IV) Clinical reasons for changes/cross-over with detail; it is anticipated, and will be reinforced at site-specific training, that cardiotocography (CTG) abnormalities would not be a reason for changing intervention as there is no evidence for superiority of one intervention over the other in such context.

It is encouraged that the first rotational method is used appropriately with adherence to key steps that maximise effectiveness. If the first rotational method fails, the accoucheur can decide if a second rotational method or a Caesarean section is necessary, and must record the reason(s) for this decision.

Should the participant request or the obstetrician think it clinically necessary to use another method (other than the allocated intervention), this will take precedence over the study, with the needs of the woman and her baby being paramount at all times.

8. OUTCOME MEASURES AND TRIAL PROCEDURES

8.1. Pilot Stage of Trial Outcomes

Trial Outcomes

All the main trial outcomes will be collected in the pilot stage and will be included in the analysis.

Progression Criteria

The decision to continue to a full trial will be decided by pre-defined independent stop-go criteria (red, amber, green (RAG) traffic lights) and supplemented with the findings from the pilot qualitative process evaluation.

8.1.1	Table for the stop-go	criteria for progressio	n from the pilot phase to full ti	rial
0.1.1	Table for the stop Bo			

Pilot (9 months)	Red	Amber	Green
Trial recruitment	<80%	80-99%	≥100%
Recruitment rate/ site/ month	<5	5-6	>6
Number of sites opened (staggered)	<9	9-11	12
Total number of participants recruited	<350	350-432	≥437
Adherence of women to randomised procedure	<90%	90-95%	>95%
Follow-up of women randomised – 3 months	<80%	80-95%	>95%
Written consent not received for women randomised	>10%	5-10%	<5%

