5.3 Consent process

Postnatally (prior to discharge, usually within 24-48 hours), a full patient information sheet will be provided to these women who verbally consented, and written consent will be sought for the use of data already collected, for participation in follow-up, and for participation in qualitative work (in the pilot) if applicable.

- Following informed verbal consent there will be automated telephone randomisation. Telephone randomisation has been shown to be efficient and pragmatic in several intrapartum trials in our experience. We have kept the number of minimisation factors to the minimum to enable an efficient and rapid randomisation process. Most of the clinicians in our national survey perform rotational deliveries in theatre which will increase the chances of recruiting – there is, in such deliveries, more time and more personnel available compared to deliveries in the labour ward room. In addition to telephone randomisation, we could also offer the option to randomise the patient via an internet-based portal. We have accounted for any missed opportunities in the very conservative estimates of recruitment rates (on average six women per site per month). Using an adaptive approach, we will monitor the randomisation process during the pilot period and amend as necessary based on the process evaluation.
- It will be the responsibility of the Principal Investigator (PI) to obtain written informed consent for each participant. This task can be delegated by the PI to other members of the local research team, most likely a Research Midwife, if local practice allows and this responsibility has been documented in the site signature and delegation log.

- Where a patient gives verbal consent and is randomised but does not give written consent anonymised data will be collected on the Day 0, 48 Hour Follow Up and Neonatal CRFs only (please see Section 5.3 for further details)
- Additional consent will be taken in the pilot for the **qualitative work** with women, partners, and healthcare professionals: interviews and audio recordings etc.

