8.1.2. Predicted site and patient recruitment for pilot phase

	Month	# Sites open	# Recruits per month	Cumulative total recruited per month
	Nov-21	1	0	0
	Dec-21	3	17	17
se	Jan-22	6	37	52
Phase	Feb-22	9	51	105
Pilot I	Mar-22	9	52	157
Pil	Apr-22	12	70	227
	May-22	12	70	297
	Jun-22	12	70	367
	Jul-22	12	70	437

RAG Criteria:

- *Green Light:* If all green criteria are met, we will proceed to a full trial with the protocol unchanged (unless there is a clear message from the process evaluation that would improve the protocol).
- Amber Light: If one or more of amber criteria are met, we will adapt the protocol with feedback from the Process Evaluation and our experience; and assess whether adaption of the protocol requires an extension of the internal pilot and further feasibility study. This plan was supported strongly by the Intrapartum Care Clinical Study Group.

• *Red Light:* If one or more of these criteria are met, we would discuss with the Trial Steering Committee whether proceeding with the trial is feasible.

Qualitative process evaluation data

We will collect data to explore the feasibility, acceptability and appropriateness of the trial processes (including consent) and interventions for women and healthcare professionals, in order to support and inform decision-making around progression to a full trial.

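### The green cut-off for pilot recruitment rate (above 6 per site per month) exceeds the protocol's own projection (5.75 to 5.83) and its planned average of six, so a pilot exactly on plan is graded amber

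*Protocol*

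**What the plan says.** The stop-go table in Protocol section 8.1.1 has three linked recruitment rows, printed in the order red, amber, green:

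- "Recruitment rate/ site/ month <5 5-6 >6"
- "Total number of participants recruited <350 350-432 ≥437"
- "Trial recruitment <80% 80-99% ≥100" (per cent)

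The row at issue is the first, "Recruitment rate/ site/ month". A fourth row makes 12 opened sites green, 9 to 11 amber and fewer than 9 red.

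Section 8.1.2 gives the month-by-month projection behind these targets, with sites open, recruits in the month, and a column headed "Cumulative total recruited per month" that ends at 437. It then states the rules. Green needs every row to be green. For amber, "If one or more of amber criteria are met, we will adapt the protocol", and the team also assesses whether the pilot should be extended. One red row leads to a discussion with the Trial Steering Committee about feasibility.

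Section 5.3 (Consent process) describes the planning assumption as "very conservative estimates of recruitment rates (on average six women per site per month".

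**The concern.** The total, percentage and site rows are set so that delivering the projection is green. The rate row should then be green for the same performance, because the projection fixes both the number of women and the number of sites open each month. It is not: the projected rate lies inside the amber band, and so does the planned average of six.

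A progression rule fixed in advance is meant to settle how on-plan performance will be judged before the data are seen. Here, delivering the plan in full triggers the amber actions. The team would have to adapt a protocol that recruited as intended, or argue after the event that the rate row should be set aside.

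**Working it through.** **Inputs** (section 8.1.2, as printed):

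| Month | Sites open | Recruits | Printed cumulative | Recruits / sites |
|---|---|---|---|---|
| Nov-21 | 1 | 0 | 0 | 0 |
| Dec-21 | 3 | 17 | 17 | 5.67 |
| Jan-22 | 6 | 37 | 52 | 6.17 |
| Feb-22 | 9 | 51 | 105 | 5.67 |
| Mar-22 | 9 | 52 | 157 | 5.78 |
| Apr-22 | 12 | 70 | 227 | 5.83 |
| May-22 | 12 | 70 | 297 | 5.83 |
| Jun-22 | 12 | 70 | 367 | 5.83 |
| Jul-22 | 12 | 70 | 437 | 5.83 |

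**1. The protocol's own total.** 0 + 17 + 37 + 51 + 52 + 4 × 70 = 437. This reproduces the printed figure.

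**2. Site-months.** 1 + 3 + 6 + 9 + 9 + 4 × 12 = 76.

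**3. Projected rate = recruits / site-months.**

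- Whole pilot: 437/76 = 5.75.
- Without November: 437/75 = 5.83.
- All 12 sites open: 70/12 = 5.83.

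All three fall in the amber band. As printed, only January exceeds 6. Rounding to six does not help, because exactly six is amber.

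**4. Colours for a pilot exactly on plan.** Total 437: green. Percentage 100%: green. Sites 12: green. Rate 5.75: amber. The overall light is amber even if every remaining row is green.

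**5. Women needed for green on rate, with sites on schedule.** More than 6 × 76 = 456, so at least 457, and 457/437 = 104.6%. Without November, more than 6 × 75 = 450, so at least 451, and 451/437 = 103.2%.

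**6. Sensitivity to the way sites are counted.** At 437 women, green on rate needs fewer than 437/6 = 72.8 site-months.

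- Counting sites from mid-month gives 70 site-months: 437/70 = 6.24, green.
- Counting them from the following month gives 64: 437/64 = 6.83, green.
- In months when the site count did not change from the month before, the convention makes no difference: March 52/9 = 5.78, and May to July 5.83. These remain amber.

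**7. Red cut-off.** Below 5 on 76 site-months means fewer than 5 × 76 = 380 women, and 380/437 = 87.0%. The total row turns red below 350, and 350/437 = 80.1%. The rate that matches 350 is 350/76 = 4.61. On 70 site-months, 350/70 = 5.0 and the two red cut-offs coincide.

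**8. Gap in the bands.** Totals of 433 to 436 have no colour. They are 433/437 = 99.1% to 436/437 = 99.8%, which also lie between the printed amber and green percentage bands.

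**9. January row.** 17 + 37 = 54, but 52 is printed. Either of two readings restores consistency:

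- Cumulative 54 with recruits as printed: 54 + 51 = 105.
- Recruits of 35 in January and 53 in February: 17 + 35 = 52 and 52 + 53 = 105. These are close to 5.83 per site (6 × 5.83 = 35.0; 9 × 5.83 = 52.5).

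The final total is 437 on both.

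**The case against.** **The denominator is not defined.** This is the strongest objection. With staggered opening, a site counted for a whole month may have recruited for only part of it. On a mid-month count the rows agree at both ends (6.24 for 437 women, 5.0 for 350). That stands as a reason to call the 457 and 380 figures conditional. It does not rescue the green cut-off. The protocol states no such convention, its table sets same-month sites beside same-month recruits at 5.67 to 6.17 in every recruiting month, and the months with a constant site count run at 5.78 to 5.83.

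**The rate row may be a deliberate stretch target.** Nothing says so, and section 5.3 presents its average of six as conservative.

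**The consequences are mild.** This stands in part. Amber means adaptation and an assessment of extension, red means a discussion, and the qualitative findings also inform the decision.

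Three stronger readings are tempting but unsupported:

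- A reader might infer that an on-target pilot could turn red. It cannot. With sites on schedule, red on rate needs fewer than 380 women, about 87% of target.
- A reader might infer that totals of 350 to 379, red on rate but amber on total, are a contradiction. The criteria are stated to be independent and one red row decides, so the outcome is defined. One row may be stricter than another by design.
- A reader might infer that the rate row is redundant. It is not. Site-months are not a criterion, only the number of sites opened. The rate row separates slow site opening from poor recruitment at open sites.

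**Conclusion.** The point holds for the green cut-off. Green above 6 is inconsistent with the projected 5.75 (5.83 with all 12 sites open) and with the planned average of six. A pilot that meets the targets of 437 women and 12 sites exactly and on schedule is amber overall.

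The excess is small: at least 457 women, 104.6% of target. That figure assumes sites open as projected and are counted in the month shown. If sites opened late, 437 women could be green on rate, but the site schedule would then have been missed.

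At the lower end there is a question and no established error: red on rate falls at about 87% of the projected rate, against 80% for total recruitment, and the protocol does not say whether that is intended. The uncoloured totals and the January mismatch are minor. The documents do not show which January cell is wrong, and 437 is unaffected. No estimand, analysis, sample size or safety rule is touched.

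**What to change.** 1. Keep the rate row and state how site-months are counted when sites open at different times.
2. Set the green cut-off at or below the projected rate on that count, for example 5.75 or more on 76 site-months, with amber running up to it. If another counting convention is adopted, recompute the cut-off from the same projection.
3. Confirm whether red below 5 is meant to be stricter than the 80% rule for total recruitment. If it is, say so. If it is not, the matching value on 76 site-months is 350/76 = 4.61.
4. Close the gap: total amber 350 to 436, and percentage amber 80 to below 100%.
5. Reconcile the January and February cells against the source projection, without presuming which one is wrong.

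The cost is one table edit and a sentence on counting, agreed with the Trial Steering Committee and the funder.
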